8.3 Concomitant Therapy

8.3.1 Medications used during the course of the study should be documented.

8.3.2 *Prohibited Concomitant Therapy:*

The administration of concurrent medications intended to treat the primary cancer is not allowed during protocol therapy. This includes any chemotherapy, investigational agent, biologic agent or other anti-tumor agents. Radiation therapy is also prohibited.

8.3.3 Patients should be strongly discouraged from taking any “alternative” or “naturopathic” medications since these agents may interact with study treatment. Any use of these medications should be at the judgment of the treating physician and should be documented in the patient’s medical record.

8.3.4 Hematopoietic growth factors and transfusions are allowed.

9.0 STUDY CALENDAR

Required Studies	Screening (within 4 weeks of initiation of treatment)	During treatment	Post Therapy	Follow-up
Physical				
Medical History	X			
Physical Exam	X	X ⁴	X ⁶	X ⁷
Performance Status	X	X ⁴	X ⁶	
Clinical Disease Assessment	X	X ⁴	X ⁶	
Adverse Event Assessment	X	X ⁴	X ⁶	
EKG	X			
Lab				
CBC and differential	X	X ⁴	X ⁶	
Serum creatinine, total bilirubin, SGOT (AST), electrolytes, glucose	X	X ⁴	X ⁶	
Albumin, LDH	X		X ⁶	
Bone marrow studies	X ¹	X ¹		
Pregnancy test	X ²			
Pathologic studies	X			
Radiology				
CT (preferred) or MRI Chest, abdomen and pelvis	X	X ⁵	X ⁶	
FDG-PET (skull base to proximal femur)	X ³	X ⁵		

¹ Bone marrow studies include aspirate and unilateral or bilateral biopsy and should be performed at screening unless approved by the Sponsor-Investigator or Lead Sub-Investigator. If all bone marrow studies are negative at screening, these do not need to be repeated. If bone marrow status is unknown or positive at screening, patients will need to have a bone marrow study to confirm a suspected CR.

² Pregnancy test is only required in women of childbearing potential.

³ May be obtained up to 8 weeks in advance of initiation of therapy (provided no additional anti-cancer therapies are administered during the interval). A Deauville score should be assigned [19].

⁴ At the beginning of therapy (within 3 days), on completion of every cycle (+/- 3 days) during first 9 cycles, then on completion of every 4 cycles (+/- 6 days) thereafter. For the first day of therapy, pre-entry H&P, PS, disease assessment, and adverse event assessment may be used (these do not need to be repeated within 3 days) and labs done within 14 days are acceptable.

⁵ During treatment restaging CT (preferred) or MRI will be performed on completion of every 3 cycles of therapy (+/- 6 days) during the first 9 cycles and on completion of every 8 cycles of therapy (+/- 12 days) thereafter, or as indicated to evaluate clinical suspicion of disease progression. Restaging PET/CT will be performed once during therapy on completion of the first 6 cycles (+/- 6 days). A Deauville score should be assigned [19] when restaging PET is performed.

⁶ Post therapy studies should be done within 28 days after the last dose of ibrutinib. A CT (preferred) or MRI will be obtained if prior imaging was > 21 days of therapy's completion.

⁷ Routine, long-term follow-up should be done approximately every 3 months or as clinically indicated. This can be done in conjunction with the patient's local MD; patients do not need to return to the SCCA. Long-term follow-up will assess survival and disease progression for up to 5-years after completion of treatment; subjects will be contacted until death, subject withdrawal of consent, lost to follow-up, or study termination by the sponsor-investigator, whichever occurs first.

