Appendix D: The Lugano Response Classification [20]

Response and Site	PET-CT-Based Response	CT-Based Response
Complete	Complete metabolic response	Complete radiologic response (all of the following)
Lymph nodes and extralymphatic sites	
Score 1, 2, or 3* with or without a residual mass on 5PS[†]
 
It is recognized that in Waldeyer's ring or extranodal sites with high physiologic uptake or with activation within spleen or marrow (eg, with chemotherapy or myeloid colony-stimulating factors), uptake may be greater than normal mediastinum and/or liver. In this circumstance, complete metabolic response may be inferred if uptake at sites of initial involvement is no greater than surrounding normal tissue even if the tissue has high physiologic uptake
	
Target nodes/nodal masses must regress to ≤ 1.5 cm in LD_i
 
No extralymphatic sites of disease

Nonmeasured lesion	Not applicable	Absent
Organ enlargement	Not applicable	Rgress to normal
New lesions	None	None
Bone marrow	No evidence of FDG-avid disease in marrow	Normal by morphology; if indeterminate, IHC negative
Partial	Partial metabolic response	Partial remission (all of the following)
Lymph nodes and extralymphatic sites	Score 4 or 5 [†] with reduced uptake compared with baseline and residual mass(es) of any size	$\geq 50\%$ decrease in SPD of up to 6 target measurable nodes and extranodal sites
	At interim, these findings suggest responding disease	When a lesion is too small to measure on CT, assign 5 mm \times 5 mm as the default value
	At end of treatment, these findings indicate residual disease	When no longer visible, 0 \times 0 mm
		For a node > 5 mm \times 5 mm, but smaller than normal, use actual measurement for calculation
Nonmeasured lesions	Not applicable	Absent/normal, regressed, but no increase
Organ enlargement	Not applicable	Spleen must have regressed by $> 50\%$ in length beyond normal
New lesions	None	None
Bone marrow	Residual uptake higher than uptake in normal marrow but reduced compared with baseline (diffuse uptake compatible with reactive changes from chemotherapy)	Not applicable

Response and Site	PET-CT-Based Response	CT-Based Response
	allowed). If there are persistent focal changes in the marrow in the context of a nodal response, consideration should be given to further evaluation with MRI or biopsy or an interval scan	
No response or stable disease	No metabolic response	Stable disease

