Target nodes/nodal masses, extranodal lesions	Score 4 or 5 with no significant change in FDG uptake from baseline at interim or end of treatment	< 50% decrease from baseline in SPD of up to 6 dominant, measurable nodes and extranodal sites; no criteria for progressive disease are met
Nonmeasured lesions	Not applicable	No increase consistent with progression
Organ enlargement	Not applicable	No increase consistent with progression
New lesions	None	None
Bone marrow	No change from baseline	Not applicable
Progressive disease	Progressive metabolic disease	Progressive disease requires at least 1 of the following
Individual target nodes/nodal masses	Score 4 or 5 with an increase in intensity of uptake from baseline and/or	PPD progression: An individual node/lesion must be abnormal with: LDi > 1.5 cm and Increase by \geq 50% from PPD nadir and An increase in LDi or SDi from nadir 0.5 cm for lesions \leq 2 cm 1.0 cm for lesions $>$ 2 cm In the setting of splenomegaly, the splenic length must increase by $>$ 50% of the extent of its prior increase beyond baseline (eg, a 15-cm spleen must increase to $>$ 16 cm). If no prior splenomegaly, must increase by at least 2 cm from baseline New or recurrent splenomegaly
Extranodal lesions	New FDG-avid foci consistent with lymphoma at interim or end-of-treatment assessment	New or clear progression of preexisting nonmeasured lesions
Nonmeasured lesions	None	New or clear progression of preexisting nonmeasured lesions
New lesions	New FDG-avid foci consistent with lymphoma rather than another etiology (eg, infection, inflammation). If uncertain regarding etiology of new lesions, biopsy or interval scan may be considered	Regrowth of previously resolved lesions A new node $>$ 1.5 cm in any axis A new extranodal site $>$ 1.0 cm in any axis; if $<$ 1.0 cm in any axis, its presence must be unequivocal and must

Response and Site	PET-CT-Based Response	CT-Based Response
		be attributable to lymphoma Assessable disease of any size unequivocally attributable to lymphoma
Bone marrow	New or recurrent FDG-avid foci	New or recurrent involvement

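### Does the calendar's marrow-confirmation rule conflict with the PET-based definition of complete response in Appendix D?

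*Combined protocol and SAP*

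**What the plan says.** Section 10.3 adopts the 2014 Lugano criteria, set out in Appendix D as a PET-CT column and a CT column.

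- **CR, PET-CT column:** score 1, 2 or 3 "with or without a residual mass on 5PS", no new lesions and, for marrow, "No evidence of FDG-avid disease in marrow". No marrow sample is requested.
- **CR, CT column:** marrow must be "Normal by morphology; if indeterminate, IHC negative".
- **PR, PET-CT column:** score 4 or 5 "with reduced uptake compared with baseline and residual mass(es) of any size".
- **No response, PET-CT column:** "Score 4 or 5 with no significant change in FDG uptake from baseline at interim or end of treatment".
- **Stable disease, CT column:** less than a 50% "decrease from baseline in SPD of up to 6 dominant, measurable nodes and extranodal sites", with no progression criterion met.

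In the study calendar, footnote 1 exempts patients whose screening marrow was negative. For the rest it says: "If bone marrow status is unknown or positive at screening, patients will need to have a bone marrow study to confirm a suspected CR". Screening marrow studies "should be performed at screening unless approved by the Sponsor-Investigator or Lead Sub-Investigator", so an unknown status can arise by design. Footnote 5 schedules one on-treatment PET/CT, after cycle 6, and CT or MRI after cycles 3, 6 and 9.

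Section 10.6 has a category of unknown status for incomplete or inconsistent assessment. Section 10.7 defines marrow as positive, negative or indeterminate without linking these to a response category. CR rate is a secondary objective (1.2.3), and ORR is CR plus PR (11.4).

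**The concern.** At the cycle-6 PET/CT the natural column to use is the PET-CT one, and it grants CR without a marrow sample. Footnote 1 asks for one if marrow was positive or unknown at screening. Take a patient with positive screening marrow, score 2 at cycle 6, no avid marrow, and a repeat marrow that is still positive or was never done. Appendix D read alone gives CR; footnote 1 does not.

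There is also no obvious place to put this patient. PET-CT partial response and no response both need a score of 4 or 5. The CT column could give PR or SD, and Section 10.6 could give unknown. If two analysts chose differently, they would report different CR rates. An ORR close to the 30% mark in Sections 11.1 and 11.4 might fall on either side of it.

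Some cross-references add to the unease. Section 11.1 twice sends the reader to 10.2 (PET scans) for response definitions. Section 7.4.1 cites 10.6 for documented progression, although 10.6 covers cases where progression has not been documented.

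**Working it through.** The plan states no figure to reproduce here. The check compares the passages and then counts patients.

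**1. Do the rules collide?** Take a patient with score 1 to 3, no new lesions and no avid marrow at cycle 6:

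| Screening marrow | Repeat marrow | PET-CT column alone | With footnote 1 |
|---|---|---|---|
| Negative | Not required | CR | CR |
| Positive or unknown | Negative | CR | CR, confirmed |
| Positive or unknown | Indeterminate, IHC negative | CR | Meets the CT column's marrow test |
| Positive or unknown | Positive | CR | Not confirmed |
| Positive or unknown | Not done | CR | Not confirmed |

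Only the last two rows differ. In both, the footnote's condition has not been met, and a patient can satisfy both rules at once. The footnote calls such a CR suspected, so imaging alone does not settle it in this subgroup. At CT-only visits nothing differs in substance, because the CT column already requires normal marrow.

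**2. Which categories are open to an unconfirmed CR?** PET-CT partial response and no response are closed (score 4 or 5 needed). Three remain:

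- PR: by the CT column if SPD fell by at least 50% and its other conditions hold, or as a simple step down from CR.
- SD: by the CT column if SPD fell by less and there is no progression.
- Unknown: by a broad reading of 10.6.

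**3. Size.** Inputs: N = 20 (estimate, Section 11.3); ORR mark 30%, or 0.30 × 20 = 6 responders. One patient is 1/20 = 5 points. Assume for illustration 3 PET-based CRs and 3 PRs, with k of the CRs unconfirmed and no response or SD at another visit for those k:

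| k | CR rate, PET-CT column alone | CR rate, footnote 1 applied: (3−k)/20 | ORR if PR | ORR if SD, or unknown kept in denominator: (6−k)/20 | ORR if unknown and excluded: (6−k)/(20−k) |
|---|---|---|---|---|---|
| 0 | 15% | 15% | 30% | 30% | 30% |
| 1 | 15% | 10% | 30% | 25% | 5/19 = 26.3% |
| 2 | 15% | 5% | 30% | 20% | 4/18 = 22.2% |
| 3 | 15% | 0% | 30% | 15% | 3/17 = 17.6% |

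Disease control (ORR plus SD) is unchanged if the patient is PR or SD. It falls by 5 points per patient if the patient is unknown and kept in the denominator.

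**4. Against sampling error.** Exact (Clopper-Pearson) 95% intervals: 3/20 gives 3.2% to 37.9%; 6/20 gives 11.9% to 54.3%.

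**5. Who is exposed?** A patient must (a) still be on treatment at cycle 6, 6 × 21 = day 126; (b) have score 1 to 3; (c) have had positive or unknown marrow at screening; and (d) lack a clearing repeat marrow. The documents do not give the number who meet all four.

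**The case for a change.** The best case for a change is that the subgroup is foreseeable. Screening marrow can be waived, and Section 5.1.7 sets separate neutrophil and platelet limits for patients with marrow involvement. Footnote 1 sits in the calendar and Section 10 never refers to it, so someone programming response from Section 10 could miss it. Even after accepting that the footnote governs, the fallback category is unstated, and 10.6 adds a candidate without settling the matter. With 6 responders in 20, one patient placed below PR takes ORR from 30% to 25%.

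The factual part stands: no visible sentence names the category of an unconfirmed CR, and Section 10 does not cite the footnote. The 2014 publication that Section 10.3 relies on is not in the documents and may cover the point.

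It does not follow that a stated rule gives a wrong result. An analyst who reports CR for a patient needing confirmation has skipped a mandatory step, so the two readings are not equally faithful to the plan. Stepping an unconfirmed CR down to PR is a sensible way to fill the gap, and it leaves ORR and disease control untouched.

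A fixed rule would not be neutral either. Counting as PR everyone without a negative marrow would demote an indeterminate, IHC-negative marrow that the CT column accepts for CR. It would also make a responder of a patient who is SD by CT and still marrow-positive.

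**Conclusion.** No change to the plan follows. The footnote adds a confirmation step to the imaging definition for patients with positive or unknown screening marrow. What is left is an unwritten fallback category for a subgroup defined by four joint conditions.

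The direct effect is on the CR rate, at 5 points per patient if enrolment is 20. That endpoint is secondary, its analysis is mainly descriptive, and it is none of the three success criteria in Section 11.1. ORR could move only if such a patient were classed SD or unknown, and disease control only if unknown, in each case without a qualifying result at another visit. Section 11.1 offers two other routes to success, and Section 11.4 says only that expansion may be recommended.

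The pointers in 11.1 and 7.4.1 are clerical slips. Section 10.3 is headed as the response criteria, so a reader finds the definitions without them.

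The counts in the illustration (3 CR, 3 PR, and 0 to 3 unconfirmed) are assumptions. The conclusion rests on the analyst applying footnote 1 as written and on the estimated N of 20.

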10.0 CRITERIA FOR EVALUATION AND ENDPOINT DEFINITIONS

Definitions of Disease, Criteria for Evaluation and Endpoint Definitions – response will be based on standard criteria for lymphoid malignancies .

10.1 Selection of Indicator (Target) Lesions

Up to six of the largest dominant nodes or tumor masses selected according to all of the following:

- Clearly measurable in at least two perpendicular dimensions
Abnormal lymph nodes are those that are either
>15 mm in the greatest transverse diameter (GTD) regardless of the short axis diameter, or
> 10 mm in short axis diameter regardless of long axis
- If possible, they should be from disparate regions of the body
- Should include mediastinal and retroperitoneal areas of disease whenever these sites are involved
- Extranodal lesions within the liver or spleen must be at least 1.0 cm in two perpendicular dimensions.

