5.0 ELIGIBILITY CRITERIA

5.1 Inclusion Criteria

- 5.1.1 Patients must have histologically confirmed transformed indolent B-cell non-Hodgkin lymphoma that is relapsed or refractory to at least one line of therapy.
- 5.1.2 Patients must have a CT (preferred) or MRI scan of the chest, abdomen, and pelvis within 28 days of enrollment.
- 5.1.3 Patients must have measurable disease defined as lesions greater than 1.5 cm that can be accurately measured in two dimensions by CT (preferred), or MRI.
- 5.1.4 Patients must have a PET scan within 56 days of enrollment.
- 5.1.5 Patients must have an ECOG performance status of 0 to 2 (See Appendix B).
- 5.1.6 Patients must be 18 years of age or older.

5.1.7 Hematology values must be within the following limits independent of growth factor or transfusion support:

5.1.7.1 Absolute neutrophil count (ANC) $\geq 1000/\text{mm}^3$ or $\geq 750/\text{mm}^3$ in the setting of marrow involvement by disease.

5.1.7.2 Platelets $\geq 50,000/\text{mm}^3$ or $\geq 30,000/\text{mm}^3$ in the setting of marrow involvement by disease or splenomegaly due to disease.

5.1.8 Biochemical values within the following limits:

5.1.8.1 Alanine aminotransferase (ALT) and aspartate aminotransferase (AST) $\leq 3 \times$ upper limit of normal (ULN)

5.1.8.2 Total bilirubin $\leq 1.5 \times$ ULN unless bilirubin rise is due to Gilbert's syndrome or of non-hepatic origin

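### Section 10.1's short-axis alternative admits target nodes that Appendix D already treats as complete-response size, which can move a CT assessment between PR and SD in either direction

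*Combined protocol and SAP*

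**What the plan says.** **Target selection (section 10.1).** Targets are "Up to six of the largest dominant nodes or tumor masses selected according to all of the following". The general requirement is "Clearly measurable in at least two perpendicular dimensions". A node counts as abnormal on either of two grounds. The first is a long axis above 15 mm, whatever the short axis. The second is "> 10 mm in short axis diameter regardless of long axis". Extranodal liver or spleen lesions need at least 1.0 cm in two dimensions.

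**Entry (section 5.1.3).** "Patients must have measurable disease defined as lesions greater than 1.5 cm that can be accurately measured in two dimensions".

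**Response (section 10.3 and Appendix D, CT column).** For complete response, "Target nodes/nodal masses must regress to" a longest diameter (LDi) of 1.5 cm or less, with no short-axis condition. Partial response needs an SPD fall of at least 50% over up to six measurable target sites. A smaller fall without progression is stable disease. For progression of a single lesion, "An individual node/lesion must be abnormal with: LDi > 1.5 cm", together with growth conditions.

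**Use (sections 11.1 and 11.4).** ORR is the primary measure, with a 30% bar. Reaching it may lead to a recommendation to add 20 patients. Estimated enrollment is 20.

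**The concern.** The long-axis ground in 10.1 agrees with Appendix D's 1.5 cm limit. The short-axis ground does not. A 14×12 mm node may be chosen as a target under 10.1, yet it is at Appendix D's complete-response size before any treatment, and it lies below the size that 5.1.3 calls measurable.

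Once such a node is in the SPD it affects the 50% rule. If it does not change, it dilutes a real halving of the larger disease. If it shrinks, it can lift a lesser reduction over the line. PR counts in ORR and SD does not, so the choice of nodes reaches the primary measure and the expansion rule.

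**Working it through.** The plan gives no alpha, power or null rate to reproduce. Its bar is 30% of an estimated 20 patients: 0.30 × 20 = 6 responders.

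**Which nodes are affected.** Short axis above 10 mm and long axis of 15 mm or less. A node with a longer long axis satisfies all three passages, taking the limit in 5.1.3 as the longest dimension.

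**Inputs.** The 50% SPD rule, the 1.5 cm limit and the 5×5 mm default for a lesion too small to measure come from Appendix D. The lesion sizes are my assumptions, because the documents give none.

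**PR becomes SD.** One node shrinks from 25×20 to 16×15 mm, and one 14×12 mm node is unchanged.
- Larger node alone: 500 to 240, a fall of 260/500 = 52.0%, PR.
- Both nodes: 500 + 168 = 668 to 240 + 168 = 408, a fall of 260/668 = 38.9%, SD.

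**SD becomes PR.** The 25×20 node shrinks to 18×15 mm, and the 14×12 node falls to the 5×5 default.
- Larger node alone: 500 to 270, a fall of 230/500 = 46.0%, SD.
- Both nodes: 668 to 270 + 25 = 295, a fall of 373/668 = 55.8%, PR.

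**How wide the affected band is.** Let L be the baseline SPD of lesions over 15 mm, S that of the small nodes, w = S/(L + S), and r the fractional fall in L.
- Small node unchanged: the total fall is r(1 − w), so PR becomes SD when 0.5 ≤ r < 0.5/(1 − w).
- Small node to 5×5 mm: SD becomes PR when 1 − [0.5(L + S) − 25]/L ≤ r < 0.5.

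With one 14×12 mm node (S = 168):

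| Larger lesion (mm) | L | w | r for PR to SD | r for SD to PR |
|---|---|---|---|---|
| 25×20 | 500 | 25.1% | 50.0–66.8% | 38.2–50.0% |
| 40×30 | 1200 | 12.3% | 50.0–57.0% | 45.1–50.0% |
| 60×50 | 3000 | 5.3% | 50.0–52.8% | 48.0–50.0% |
| 100×80 | 8000 | 2.1% | 50.0–51.0% | 49.3–50.0% |

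With five unchanged 14×12 mm nodes beside 60×50 mm, S = 840, w = 840/3840 = 21.9%, and the PR-to-SD band is 50.0–64.0%.

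**Where ORR does not move.** A 20×15 mm node shrinks to 13×10 mm beside two unchanged 14×12 mm nodes. The SPD falls are 170/300 = 56.7% without the small nodes and 170/636 = 26.7% with them. Every target node is then at 15 mm or less, so both target sets are at complete-response size. If the other CR conditions hold, the patient is a responder either way.

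**Weight of one patient.** One swap moves ORR by 1/20 = 5 points: 5/20 = 25% misses the bar and 6/20 = 30% meets it. If the true ORR is 30%, the chance of exactly 5 responders is 0.762 − 0.584, about 0.18, and of exactly 6 is 0.584 − 0.392, about 0.19. These are the counts at which one upward or one downward swap would decide the bar.

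**The case against.** The strongest reply is that the protocol, read literally, gives one answer: 10.1 selects, Appendix D scores, and 5.1.3 governs entry only. That stands. A reader might infer that the plan classifies the same scans in two ways. It does so only if someone carries the 5.1.3 limit into Appendix D's use of the word measurable, and no passage tells them to. The point is that the single literal rule fits badly with the adopted standard.

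A reader might also infer that 10.1 forces small nodes in whenever fewer than six larger lesions exist. It does not. Six is a ceiling, and selection favors the largest dominant disease. Such nodes may be chosen, and 10.1's preference for disparate regions and for involved mediastinal and retroperitoneal sites can favor that.

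Nor does the complete-response mismatch by itself change ORR. It bears on CR versus PR, and both count. The PR/SD effect comes from which nodes enter the SPD. The progression limit adds little too: a node with short axis above 10 mm that grows by the required 0.5 cm from baseline has already passed 1.5 cm.

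Finally, the PET-CT column does not use SPD, and disease control rate and PFS do not depend on the PR/SD split. All of that is right and limits the reach. It does not remove the point: on-treatment PET is scheduled once, after six cycles. The other scheduled restagings are CT or MRI, and the documents do not say which column governs.

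**Conclusion.** The concern holds in a limited form. The short-axis alternative in 10.1 is inconsistent with Appendix D's 1.5 cm limit, and it can misplace a patient between PR and SD on CT. The effect is material beside small lesions (52.0% against 38.9%) and slight beside bulky disease (a band of 2.8 percentage points beside 60×50 mm). It needs a node in the narrow affected size range that is actually chosen as a target.

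The documents do not support a claim that ORR is biased in a known direction, since both swaps are possible. They do not support any estimate of how many patients are affected. The sizes used here are illustrative, and the 5-point step assumes 20 patients analysed. The correction is still worthwhile because one patient can decide the 30% bar and it costs almost nothing.

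**What to change.** In 10.1, delete the short-axis alternative and require a nodal target to have a longest diameter above 15 mm. Add that nodes with LDi of 15 mm or less at baseline count as normal size for CR and PR under Appendix D, and matter only if they meet its progression criteria.

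Do not class these nodes as non-measured disease. Appendix D requires non-measured lesions to be absent for CT complete response, so a persisting 14×12 mm node could then block a CR that it does not block today.

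Leave the extranodal 1.0 cm line and 5.1.3 unchanged. The complete-response size limit applies to nodes, whereas CT complete response requires no extralymphatic disease at all, so the same mismatch does not arise there.

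The cost is a short wording change in 10.1, with no extra scans or readers. The downside is that some patients will have fewer target lesions. Taking 5.1.3's limit as the longest dimension, a patient who qualifies on nodal disease still has at least one nodal target.
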